Clinical trials involving molecularly targeted therapies in advanced endometrial cancer have been undertaken recently, with impressive results. Erlotinib is a small molecule inhibitor of the epidermal growth factor receptor (EGFR), which is overexpressed in 60-80% of endometrial cancers. A phase II study of erlotinib in endometrial cancer has recently completed, reporting a 12.5% overall response rate 12. Temsirolimus (CCI-779) is an inhibitor of the mammalian target of rapamycin (mTOR), a key regulator of intracellular protein translation. mTOR activation is associated with increased protein translation, progression through G1 of the cell cycle, and increased cell growth. Preliminary results of an ongoing phase II trial of CCI-779 as weekly treatment of patients with recurrent or advanced endometrial cancer have been reported in abstract form. Among the first 23 patients treated, a response rate of 31% has been demonstrated 13.

Whereas combination chemotherapy is the first-line treatment of choice for patients with advanced endometrial cancer with adequate organ function and performance status, there is no clear standard second-line treatment regimen. Evidence is available from small phase II trials to guide clinical management in this setting (see table 1). With the exception of one phase II trial of paclitaxel in previously-treated patients (RR=28%, median PFS = 4.2 months 14), second-line chemotherapy for advanced endometrial cancer has been minimally effective 15-19 20 21 22. Response rates are universally less than 20% (often less than 10%) and the majority of patients have progressive disease within 3 months.

Table 1. Phase II trials of single-agent chemotherapy in the management of advanced endometrial cancer.

\* RR for all patients in bold. RR depending on prior chemotherapy in parentheses (no prior

Agent (n)	Prior chemo	RR*	PFS	OS	Reference
Paclitaxel (15)	Yes	27%	NR	NR	(14)
Flavopiridol (26)	Yes	0	3.2 mo	NR	(15)
PLD (46)	Yes	9.5%	NR	8.2 mo	(16)
Irofulven (25)	Yes	4%	2.0 mo	9.4 mo	(18)
Cyclo (29) Ifos (32)	Yes / no	7% (0 / 14) 12% (0 / 25)	2.0 mo 1.7 mo	NR NR	(17)
Carboplatin (64)	Yes / no	13% (0 / 24)	2.8 mo	8.7 mo	(19)
Docetaxel (33)	Yes / no	31% (23 / 37)	3.9 mo	17.8 mo	(21)
Paclitaxel (23)	Yes / no	30.4% (8 / 60)	NR	NR	(22)
PLD (52)	No	11.5%	NR	10.9 mo	(20)
Erlotinib (25)	No	13%	NR	NR	(12)
CCI-779 (23)	No	26%	NR	NR	(13)

chemotherapy / prior chemotherapy)

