### **3. PATIENT SELECTION**

#### **3.1 Eligibility Criteria**

- 3.1.1 Patients must have histologically or cytologically confirmed endometrial cancer. Adenocarcinoma (endometrioid and serous / papillary serous) and carcinosarcoma (ie. malignant mixed mullerian tumor (MMMT) of the uterus will be investigated. Patients with other histologies (eg. squamous cell carcinoma or leiomyosarcoma) are excluded.
- 3.1.2 Patients must have measurable disease, defined as at least one lesion that can be accurately measured in at least one dimension (longest diameter to be recorded) as  $\geq 20$  mm with conventional techniques or as  $\geq 10$  mm with spiral CT scan. See section 10.2 for the evaluation of measurable disease. Indicator lesions must not have been previously treated with surgery, radiation therapy or radiofrequency ablation.
- 3.1.3 Previously treated patients must have evidence of progressive disease, either clinically or radiographically, as assessed by the investigator.

3.1.4 Eligible patients may have received no more than one prior cytotoxic chemotherapy regimen for recurrent, locally-advanced, or metastatic disease. If the prior chemotherapy was an anthracycline, they may have received no more than 6 cycles (or less than 450 mg/m^2 doxorubicin). Patients must have completed any previous chemotherapy a minimum of 4 weeks (or 6 weeks if the regimen contained BCNU or mitomycin) prior to study registration. Prior investigational treatment is permissible (as long as such treatment completed 4 weeks prior to registration).

3.1.5 Because no dosing or adverse event data are currently available on the use of sunitinib in patients <18 years of age, children are excluded from this study but will be eligible for future pediatric single-agent trials, if applicable.

3.1.6 Life expectancy of greater than 3 months.

3.1.7 ECOG performance status  $\leq 2$  (Karnofsky  $\square \geq 60\%$ ; see Appendix A).

3.1.8 Patients must have normal organ and marrow function as defined below:

X	leukocytes	$\geq 3,000/\text{mcL}$
X	absolute neutrophil count	$\geq 1,500/\text{mcL}$
X	platelets	$\geq 100,000/\text{mcL}$
X	hemoglobin	$\geq 100 \text{ g/L}$
X	serum calcium	$\leq 12.0 \text{ mg/dL} (\leq 3.0 \text{ mmol/L})$
X	total serum bilirubin	within normal institutional limits
X	AST(SGOT)/ALT(SGPT)	$\leq 2.5 \times$ institutional upper limit of normal
X	creatinine	within normal institutional limits
OR		

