### 12.1 Study Design/Endpoints

The primary endpoint of the study is objective response rate (ORR). ORR is defined as the rate of complete or partial response as defined by the RECIST criteria (see section 10.3). Secondary endpoints will include prolonged stable disease (as defined in sections 1 and 11.4.3) overall survival, toxicity and time to progression.

A two-stage design has been adopted for this study that judges the agent as promising based on tumor response rate. An objective response rate of 20% would be considered of interest, whereas a rate of 5% would be deemed uninteresting. For this design we will set  $\alpha \approx 0.05$  and  $\beta \approx 0.20$ .

- In the first stage, 15 patients will be accrued. If no objective responses are observed among the initial 15 evaluable patients, the study would be terminated early and declared negative.
- If there are 1 or more objective responses, the trial will continue on to a second stage, accruing an additional 15 patients.
- If at least 4 objective responses (at least 13%) are observed among the 30 evaluable patients, this agent would be considered worthy of further testing in this disease.

This design yields 86.5% (type II error=0.135) power to detect a true objective response rate of at least 20% and 0.942 (type I error=0.058) probability of a negative result if the true objective response rate is no more than 5%. The probability of stopping at the end of the first stage is approximately 0.46 and the expected sample size is 23.05 if the true objective response rate is 5%.

Data from clinical trials of single-agent chemotherapy in the salvage setting for endometrial cancer suggest a median progression-free survival from 1.8 – 3.2 months (see section 2). Assuming exponential survival, this equates to an approximate 6-month progression-free survival rate of 10-25%. Based on these statistics, we consider 6-month stable disease rate of greater than 25% (or 4 out of the first 15 patients) to be of interest, even in the absence of

objective response.

If, at the end of stage I, no objective responses are seen, but at least 4 patients demonstrate prolonged stable disease (i.e. best response of stable disease that is maintained for at least 6 months), consideration would be given to continuing accrual to the second stage. In this circumstance, a decision to continue to stage II would only be made in consultation with CTEP.

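### The 25% (4/15) stable-disease benchmark in 12.1 rests on a salvage-only PFS range that does not match Section 2 and is applied to a trial that also enrols chemotherapy-naive patients

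*Combined protocol and SAP*

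**What the plan says.** Section 12.1 states: "Data from clinical trials of single-agent chemotherapy in the salvage setting for endometrial cancer suggest a median progression-free survival from 1.8" to 3.2 months, citing Section 2, and continues: "Assuming exponential survival, this equates to an approximate 6-month progression-free survival rate of 10-25"%. From this it concludes that "we consider 6-month stable disease rate of greater than 25% (or 4 out of the first 15 patients) to be of interest", even with no objective response. If stage I shows no responses but at least 4 of 15 patients have prolonged stable disease, continuing may be considered, though "a decision to continue to stage II would only be made in consultation with CTEP".

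Section 2.1, the cited source, reports two medians above 3.2 months. The text says "With the exception of one phase II trial of paclitaxel in previously-treated patients (RR=28%, median PFS = 4.2 months 14"), and the docetaxel row of Table 1, a trial with and without prior chemotherapy, reads "31% (23 / 37) 3.9 mo 17.8 mo" (response rate, PFS, overall survival).

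On who may enrol, 3.1.4 says: "Eligible patients may have received no more than one prior cytotoxic chemotherapy regimen for recurrent, locally-advanced, or metastatic disease". Section 3.1.3 asks for evidence of progression only in previously treated patients. Patients with no prior regimen are therefore eligible.

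**The concern.** The trial has one arm, so the historical figure is the only comparator for the 6-month rate. That rate is a primary objective in 1.1 (12.1 lists it as secondary). It is also the only basis on which a trial with 0/15 responses could go on to 15 more patients.

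Two things look wrong. First, the range cannot be traced to the section it cites, and the two longest medians reported there are left out without a stated reason. Second, all patients are pooled against a salvage figure although some may be chemotherapy-naive. Table 1 suggests that case mix matters: response rates split by prior chemotherapy differ widely in every mixed trial (0/14, 0/25, 0/24, 23/37 and 8/60 percent), whichever way round the pairs are read. Section 12.3 plans no breakdown by prior chemotherapy. A pooled 6-month rate near 25% could then be read as drug effect when it reflects case mix, or an ordinary result for chemotherapy.

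**Working it through.** **Inputs.** Median PFS values come from the text and Table 1 of Section 2.1. The exponential assumption and the 4/15 criterion come from 12.1.

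**Formula.** Under exponential PFS, the 6-month rate is 0.5^(6/median).

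**The plan's own figures.**
- Lower end: 0.5^(6/1.8) = 9.9%, which reproduces the stated 10%.
- Upper end: 0.5^(6/3.2) = 27.3%, not 25%. A rate of 25% corresponds to a median of 3.0 months.
- The criterion: 4/15 = 26.7%, below 27.3%.

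**What Section 2 reports.**

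| Trial (n) | Prior chemotherapy | Median PFS, months | 6-month rate |
|---|---|---|---|
| Ifosfamide (32) | mixed | 1.7 | 8.7% |
| Cyclophosphamide (29) | mixed | 2.0 | 12.5% |
| Carboplatin (64) | mixed | 2.8 | 22.6% |
| Docetaxel (33) | mixed | 3.9 | 34.4% |
| Irofulven (25) | yes | 2.0 | 12.5% |
| Flavopiridol (26) | yes | 3.2 | 27.3% |
| Paclitaxel (text only) | yes | 4.2 | 37.1% |

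**Can 1.8–3.2 be recovered?** No selection of these rows gives it. Pretreated-only rows of Table 1 give 2.0–3.2 months, or 2.0–4.2 with the paclitaxel trial in the text. All values together give 1.7–4.2. The figure 1.8 does not appear in Section 2.

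**Mixed trials, the nearest match to 3.1.4.** The range is 8.7–34.4%. The size-weighted mean is (32 × 0.0866 + 29 × 0.125 + 64 × 0.2264 + 33 × 0.3443) / 158 = 20.4%.

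**Untreated patients only.** The three rows without prior chemotherapy (pegylated liposomal doxorubicin, erlotinib, CCI-779) list PFS as not reported, and the plan states no expected case mix. A control matched on case mix cannot be derived.

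**The paclitaxel entry.** The text gives a response rate of 28% and PFS 4.2 months for a trial in previously treated patients. The pretreated paclitaxel row of Table 1 (n = 15) gives 27% and PFS not reported.

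**What the benchmark separates.** Flavopiridol had no responses and a 3.2-month median. A drug with that 27.3% rate and a true response rate of zero would show 0/15 responses and then reach at least 4/15 with binomial probability 0.617.

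**The case against.** Leaving out the two long medians can be defended. Section 2 labels the 4.2-month paclitaxel trial an exception, and its PFS is missing from Table 1. The 3.9-month docetaxel trial is mixed, so it can be kept out of a salvage range. The text calls the conversion approximate, and rounding 27.3% to the nearest 5 points gives 25%. The rule is discretionary and needs consultation with CTEP, and the judgement of activity rests on response rate. All of this limits the consequence. It does not explain the 1.8, put any reason for the omissions in 12.1, or alter the mismatch with 3.1.4. Rounding also matters here, because it moves the top of the range from just above 4/15 to just below it.

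Two stronger readings are tempting, and the documents do not support them.

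- A reader might infer that a properly matched control is 34–37%, so that 4/15 falls below what chemotherapy achieves. But 37.1% comes from a pretreated trial, so it says nothing about admitting untreated patients, and 34.4% is the highest of four mixed arms. The mixed-trial average, about 20%, is below 4/15.
- A reader might also take the binomial chances of at least 4/15 at those rates, 0.815 at 34.4% and 0.867 at 37.1%, as the chance that an ordinary drug passes the rule. The rule applies only after 0/15 responses. Drugs with the response rates of those two trials would get there with probability 0.69^15 = 0.004 (31%) or 0.73^15 = 0.009 (27%). They would enter stage II on responses.

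**Conclusion.** The point holds as one about the stated comparator and what a rate near 25% can show. The range in 12.1 does not match the section it cites: 1.7–4.2 months (about 9–37% at 6 months) against a stated 1.8–3.2 months (10–25%). Even the stated upper end converts to 27.3%. On either range, 4/15 (26.7%) lies inside historical experience with single-agent chemotherapy, above its average and below its best trials. It cannot by itself be read as activity beyond chemotherapy. The salvage label also does not fit a population that may include chemotherapy-naive patients, and Section 2 gives no basis for a matched figure.

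The percentages assume exponential PFS in every trial. The 0.617 further assumes 15 independent, fully assessed patients and a true response rate of zero, and it is the chance of meeting the criterion for consultation, not of continuing. The two-stage response design is unaffected: its stated type I error of 0.058, power of 86.5%, early-stopping probability of 0.46 and expected sample size of 23.05 all reproduce.

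**What to change.** In Section 12.1:

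1. Restate the historical range as Section 2 reports it (1.7–4.2 months, about 9–37% at 6 months), or say why 3.9 and 4.2 months are excluded. Give the source of 1.8 if it is kept. Reconcile the paclitaxel response rate and PFS between the text and Table 1.
2. Correct the conversion of 3.2 months to 27%.
3. State that 4/15 (26.7%) lies inside the historical range and so is not evidence of activity above chemotherapy. The existing consultation with CTEP can stay as written.
4. Report the 6-month rate separately for no prior regimen and one prior regimen. Apply the salvage benchmark only to the latter, and set the pooled rate against the mixed-trial range (1.7–3.9 months, about 9–34%).

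The cost is wording and one extra breakdown, using prior-treatment information already needed for eligibility. No more patients are needed. The benchmark will look less favourable, and the subgroup rates will be imprecise: 4/15 pooled already has an exact 95% interval of 8–55%.

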## 12.2 Sample Size/Accrual Rate

Sample size: 15 (minimum) to 30 (projected maximum)

Anticipated accrual rate: 2 patients per month

## 12.3 Analysis of Secondary Endpoints

Survival statistics will be estimated using the Kaplan-Meier method. Patients will be evaluated for response according to the RECIST criteria. Standard descriptive statistics, such as the mean, median, range and proportion, will be used to summarize the patient sample and to estimate parameters of interest. Adverse events will be described using the CTCAE v3 (as described in section 7) and will be summarized in tabular form, describing all adverse events, and sub-tables describing all attributable (possibly, probably or definitely related) and all serious (grade 3 or higher) adverse events will also be constructed. All tests will be two-sided and a p-value of 0.05 or less will be considered statistically significant. 95% confidence intervals will be provided for estimates of interest where possible.

## 12.4 Reporting and Exclusions

12.4.1 **Evaluation of toxicity.** All patients will be evaluable for toxicity from the time of their first treatment with sunitinib.

12.4.2 **Evaluation of response.** All patients included in the study will be assessed for response to treatment, even if there are major protocol treatment deviations or if they are ineligible. Each patient will be assigned one of the following categories: 1) complete response, 2) partial response, 3) stable disease, 4) progressive disease, 5) early death from malignant disease, 6) early death from toxicity, 7) early death because of other cause, or 9) unknown (not assessable, insufficient data).

All of the patients who meet the eligibility criteria (with the possible exception of those who received no study medication) will be included in the main analysis of the response rate. Patients in response categories 4-9 will be considered to have a treatment failure (disease progression). Thus, an incorrect treatment schedule or drug administration will not result in exclusion from the analysis of the response rate.

All conclusions will be based on all eligible patients. Subanalyses may then be performed on the basis of a subset of patients, excluding those for whom major protocol deviations have been identified (e.g., early death due to other reasons, early discontinuation of treatment, major protocol violations, etc.). However, these

subanalyses will not serve as the basis for drawing conclusions concerning treatment efficacy, and the reasons for excluding patients from the analysis will be clearly reported.

**APPENDIX A      PERFORMANCE STATUS CRITERIA**

ECOG Performance Status Scale		Karnofsky Performance Scale	
Grade	Descriptions	Percent	Description
0	Normal activity. Fully active, able to carry on all pre-disease performance without restriction.	100	Normal, no complaints, no evidence of disease.
		90	Able to carry on normal activity; minor signs or symptoms of disease.
1	Symptoms, but ambulatory. Restricted in physically strenuous activity, but ambulatory and able to carry out work of a light or sedentary nature (e.g., light housework, office work).	80	Normal activity with effort; some signs or symptoms of disease.
		70	Cares for self, unable to carry on normal activity or to do active work.
2	In bed <50% of the time. Ambulatory and capable of all self-care, but unable to carry out any work activities. Up and about more than 50% of waking hours.	60	Requires occasional assistance, but is able to care for most of his/her needs.
		50	Requires considerable assistance and frequent medical care.
3	In bed >50% of the time. Capable of only limited self-care, confined to bed or chair more than 50% of waking hours.	40	Disabled, requires special care and assistance.
		30	Severely disabled, hospitalization indicated. Death not imminent.
4	100% bedridden. Completely disabled. Cannot carry on any self-care. Totally confined to bed or chair.	20	Very sick, hospitalization indicated. Death not imminent.
		10	Moribund, fatal processes progressing rapidly.
5	Dead.	0	Dead.

**APPENDIX B                    NEW YORK HEART ASSOCIATION CLASSIFICATION OF  
                                  CARDIAC DISEASE**

**New York Heart Association Classifications**

Clinical Evaluation of Functional Capacity of Patients  
with Heart Disease in Relation to Ordinary Physical Activity

Class	Cardiac Symptoms	Limitations	Need for Additional Rest*	Physical Ability to work**
I	None	None	None	Full time
II	Only moderate	Slight	Usually only slight or occasional	Usually full time
III	Defined, with less than ordinary activity	Marked	Usually moderate	Usually part time
IV	May be present even at rest, and any activity increases discomfort	Extreme	Marked	Unable to work

\* To control or relieve symptoms, as determined by the patient, rather than as advised by the physician.

\*\* At accustomed occupation or usual tasks.

Reference:

Bruce, R. A.: Mod. Concepts Cardiovasc. Dis. 25:321, 1956. (Modified from New York Heart Association, 1953.

**APPENDIX C**

**DRUGS KNOWN TO BE METABOLIZED BY SELECTED CYP450 ISOENZYMES**

**CYP3A4**

SUBSTRATES		INHIBITORS		INDUCERS	
Generic Name	Trade Name	Generic Name	Trade Name	Generic Name	Trade Name
Anti-neoplastics: e.g. Docetaxel Gefitinib Irinotecan	Taxotere Iressa Camptosar	Anti-arrhythmics: e.g. Amiodarone Diltiazem Quinidine	Cordarone, Pacerone Cardizem, Dilacor XR Cardioquin	Aminoglutethimide	Cytadren
Anti-virals: e.g. Amprenavir Rifampin	Agenerase Rifadin	Anti-virals: e.g. Amprenavir Indinavir Nelfinavir Ritonavir	Agenerase Crixivan Viracept Norvir	Antibiotics: e.g. Rifabutin Rifampin	Rifadin Mycobutin
Anxiolytics: e.g. Diazepam Sertraline	Valium Zoloft	Cimetadine	Tagamet	Anticonvulsants: e.g. Carbamazepine Phenytoin Pentobarbital Phenobarbital	Tegretol Dilantin Nembutal Luminal
Cyclosporine	Sandimmune	Cyclosporine	Sandimmune	Hypericum perforatum (2)	St. John's Wort
Anti-infectives: e.g. Erythromycin Tetracycline	Erythrocin Sumycin	Antibiotics: e.g. Ciprofloxacin Clarithromycin Doxycycline Enoxacin Isoniazid Telithromycin	Cipro, Ciloxan Biaxin Adoxa, Periostat Penetrex Nydrazid, INH Ketek		
Steroids: e.g. Estrogens, conjugated Estradiol Progesterone	Premarin Climara Crinone	Imatinib	Gleevec		
Haloperidol	Haldol	Haloperidol	Haldol		
Cardiovascular agents: e.g. Digitoxin Quinidine	Crystodigin Cardioquin	Diclofenac	Cataflam, Voltaren		
Anti-hypertensives: e.g. Nicardipine Verapamil	Cardene Calan, Chronovera	Vasodilators: e.g. Nicardipine Verapamil	Cardene Calan, Chronovera		
Anesthetics: e.g. Ketamine Lidocaine	Xylocaine Diprivan	Anesthetics: e.g. Lidocaine Propofol	Xylocaine Diprivan		
Nefazodone	Serzone	Anti-depressants: e.g. Nefazodone Sertraline	Serzone Zoloft		
Cocaine		Anti-fungals: e.g. Itraconazole Ketoconazole Miconazole	Sporanox Nizoral Lotrimin, Monistat		
Ketoconazole	Nizoral	Caffeine			
Sildenafil	Viagra	Grapefruit juice (1)			
Albuterol	Ventolin				
Carbamazepine	Tegretol				
Lovastatin	Mevacor				

When drugs classified as 'substrates' are co-administered with *(Sunitinib Malate)*, there is the potential for higher concentrations of the 'substrate'. When *(Sunitinib Malate)* is co-administered with compounds classified as 'inhibitors', increased plasma concentrations of *(Sunitinib Malate)* is the potential outcome. The coadministration of 'inducers' would potentially lower plasma *(Sunitinib Malate)* concentrations.

## CYP3A4

Inhibitors				
Acetominophen	Diltiazem	Lovastatin	Progesterone	
Acetazolamide	Disulfiram	Mefloquine	Propofol	
Amioderone	Docetaxel	Mestranol	Propoxyphene	
Amlodipine	Doxorubicin	Methadone	Quinidine	
Amprenavir	Doxycycline	Methimazole	Quinine	
Anastrozole	Drospirenone	Methoxsalen	Quinupristin	
Aprepitant	Efavirenz	Methylprednisolone	Rabeprazole	
Atazanavir	Enoxacin	Metronidazole	Risperidone	
Atorvastatin	Entacapone	Miconazole	Ritonavir	
Azelastine	Ergotamine	Midazolam	Saquinavir	
Azithromycin	Erythromycin	Mifepristone	Selegiline	
Betamethasone	Ethynodiol	Mirtazapine	Sertraline	
Bortezomib	Etoposide	Mitoxantrone	Sildenafil	
Bromocriptine	Felodipine	Modafinil	Sirolimus	
Caffeine	Fentanyl	Nefazodone	Sulconazole	
Cerivastatin	Fluconazole	Nelfinavir	Tacrolimus	
Chloramphenicol	Fluoxetine	Nevirapine	Tamoxifen	
Chlorzoxazone	Fluvastatin	Nicardipine	Telithromycin	
Cimetidine	Fluvoxamine	Nifedipine	Teniposide	
Ciprofloxacin	Fosamprenavir	Nisoldipine	Testosterone	
Cisapride	Glyburide	Nitrendipine	Tetracycline	
Clarithromycin	Grapefruit juice	Nizatidine	Ticlopidine	
Clemastine	Haloperidol	Norfloxacin	Tranylcypromine	
Clofazimine	Hydralazine	Olanzapine	Trazodone	
Clotrimazole	Ifosfamide	Omeprazole	Troleandomycin	
Clozapine	Imatinib	Orphenadrine	Valproic acid	
Cocaine	Indinavir	Oxybutynin	Venlafaxine	
Cyclophosphamide	Irbesartan	Paroxetine	Verapamil	
Cyclosporine	Isoniazid	Pentamidine	Vinblastine	
Danazol	Isradipine	Pergolide	Vincristine	
Delavirdine	Itraconazole	Phencyclidine	Vinorelbine	
Desipramine	Ketoconazole	Pilocarpine	Zafirlukast	
Dexmedetomidine	Lansoprazole	Pimozide	Ziprasidone	
Diazepam	Lidocaine	Pravastatin		
Diclofenac	Lomustine	Prednisolone		
Dihydroergotamine	Losartan	Primaquine		

Inducers			
Aminoglutethimide	Nevirapine	Phenytoin	Rifapentine
Carbamazepine	Oxcarbazepine	Primidone	
Fosphenytoin	Pentobarbital	Rifabutin	
St. John's wort	Phenobarbital	Rifampin	

(Adapted from Cytochrome P-450 Enzymes and Drug metabolism. In: Lacy CF, Armstrong LL, Goldman MP, Lance LL eds. Drug Information Handbook 12th ed. Hudson, OH; LexiComp Inc. 2004: 1619-1631.)

(1) Malhorta et al. (2000). *Clin Pharmacol Ther.* 69:14-23

(2) Mathijssen et al. (2002). *J Natl Cancer Inst.* 94:1247-1249  
Frye et al. (2004). *Clin Pharmacol Ther.* 76:323-329

INFORMATION ON POSSIBLE DRUG INTERACTIONS	
